### **9.10 Responsibilities of the Coordinating Center (Montefiore Medical Center) and Celgene Corporation.**

The Coordinating Center (Montefiore Medical Center) will maintain records and provide reports to Celgene Corporation for the following Adverse Experiences:

1. All serious, unexpected, adverse events,
2. Any significant increase in the frequency of serious expected adverse events, and
3. An annual progress report including number of patients accrued, date on study, date off study, vital status (alive/dead and date alive/dead).

Celgene Corporation will supply study drug, lenalidomide free of charge.

## **10. STATISTICAL CONSIDERATIONS**

### **10.1 Study Design/Endpoints**

The aim of this proposal is to provide an accurate estimate of the two-year relapse free survival rate for elderly AML patients treated with lenalidomide maintenance after autologous stem cell transplantation. With about 30 patients, the study will be able to estimate the two year relapse free survival rate with not more than 9% standard error (i.e., if the observed rate is 40%, the 95% CI will be (23%, 56%). In addition, our study will have over 80% power to conclude that the two year relapse rate is significantly reduced when patients are treated with lenalidomide, assuming 60% and 90% patients will relapse with and without lenalidomide, respectively. The observed relapse free survival rate will be calculated along with its 95% CI. A one sample test on proportion will be used to detect if the relapse free survival rate with lenalidomide is significantly higher than that without the treatment (relapse rate is expected to be >95%). Secondary analysis including Kaplan-Meier analysis on overall survival.

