**SYNOPSIS**

**BACKGROUND:** AML in patients 60 and over has a very poor prognosis. With standard induction chemotherapy and consolidation with autologous stem cell transplant a substantial proportion of patients will be able to achieve remission. Unfortunately, virtually all of those that achieve remission will relapse and die of their disease. Recently, lenalidomide has been shown to be an active agent for AML. In addition, lenalidomide has been shown to be a feasible and effective maintenance strategy for myeloma post autologous transplant. We therefore propose to study the feasibility and efficacy of lenalidomide maintenance after autologous transplant in AML.

The primary objective is to determine the safety and efficacy of maintenance lenalidomide after autologous stem cell transplant in this setting.

Secondary Objectives are to determine the progression free survival and overall survival for patients treated with this approach.

**TREATMENT:** Elderly patients with AML who have achieved morphologic remission will be treated with escalating doses of lenalidomide (starting at 10mg once daily 21 days each month) in groups of 3 until a maximum dose of 25mg once daily 21 days each month has been reached.

**Key Eligibility Criteria:** Patients must have a diagnosis of Acute Myeloid Leukemia excluding Acute Promyelocytic Leukemia (M3). Age 60-80, No uncontrolled CHF. Adequate renal and liver function. ECOG performance status  $\leq 2$ , and a life expectancy of  $> 12$  months. Patients will be excluded if they have an untransfused platelet count of  $< 75$ , are growth factor dependent, have uncontrolled infection, have HIV or HTLV-1 infection, have active CNS disease, or prior malignancy other than adequately treated non-melanoma skin cancer.

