## **2. BACKGROUND and RATIONALE**

### **2.1 Induction Therapy for Elderly AML Patients**

AML is mainly a disease of the elderly with a median age of 69 years in the white US population, and prognosis worsens every decade beginning at age 30 to 40. A report by the German Acute Myeloid Leukemia Cooperative Group studied patients 16 to 85 years

of age enrolled in two consecutive trials who had AML. In a multivariate analysis of prognostic factors, age  $\geq 60$  years was a statistically significant poor prognostic factor for complete remission, overall survival, remission duration, and relapse free survival. Population based studies have reported 3- and 5-year survival rates of only 9 to 10% and 3 to 8%, respectively, in patients over age 60, compared with 5-year survival rates of up to 50% for younger patients. Poorer outcome has traditionally been considered at least in part due to reluctance of physicians to treat this population aggressively. As such, lower levels of aggressive treatments may compound underlying prognostic differences associated with patient factors and disease biology. Recent studies have therefore focused on dose intensification of anthracyclines and/or postremission therapy. Lowenberg and colleagues compared induction therapy with daunorubicin (DNR) at a dose of 45 mg/m^2 or 90mg/m^2 in 813 patients over age 60 with previously untreated AML. Although complete response (CR) rates were improved in the group that received the higher dose of DNR (64% vs 54%, P=.002) there was no significant difference in the two induction groups with respect to overall survival (OS) and event-free survival (EFS). Thirty-day mortality was 11% to 12% in both groups. Two year probabilities of relapse after CR for the standard versus intensified DNR groups were 61% versus 54%. Of note, dose reduced anthracycline led to inferior CR rates and survival was not as good in certain subgroups of patients. As such, although the superiority of higher dose anthracycline as induction is not established in AML patients over 60 there 1) seems to be no increased toxicities with these regimens and 2) there is certainly no reason to attenuate doses of anthracycline in AML patients over 60. Doses of DNR at 60mg/m^2 or Idarubicin at 12mg/m^2 for 3 days together with cytarabine would be appropriate to use.

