peripheral blood stem cell transplant after a single cycle of cytarabine-based consolidation therapy. Leukemia free survival and overall survival at 3 years was 25% and 28% respectively. There was one death from transplant related mortality. The authors concluded that autologous transplantation of peripheral blood stem cells is well tolerated and feasible for patients  $\geq 60$  years of age with AML in first CR. Ferrara and colleagues studied sixty three patients with non-M3 AML. The median age was 69 with range between 61 and 81. Included were patients with AML secondary to myelodysplastic syndrome. The transplant related mortality was 0%. Those patients that received a transplant (n=17) had a significantly better overall survival and disease free survival when compared to those that did not undergo transplant (n=10). Oriol and colleagues evaluated the feasibility and results of autologous stem cell transplant in 258 AML patients in first CR who were over 60. The probability of 2 year leukemia-free survival was 39% for those candidate patients who underwent transplant and 22% for those that did not (p=.07). The authors concluded that autologous transplantation has a tolerable toxicity and may have a positive impact on leukemia-free survival.

In summary then a few conclusions are reasonable to make for the patient with AML: 1) Standard induction chemotherapy is feasible, and certainly there is no role to reduce the dose of anthracycline for a fit elderly patient 2) Autologous stem cell transplant may have superior anti-leukemic efficacy in the young AML patient when compared with standard consolidation chemotherapy 3) There is some suggestion that the superior antileukemic efficacy of autologous transplant may translate to benefit the elderly patient with AML as well 4) Autologous stem cell transplant is feasible in the elderly patient with AML vis a vis toxicities 5) While remissions in the elderly patient with AML are attainable, relapse is still the major obstacle to reach the goal of long term leukemia-free survival.

As such, new approaches are needed to enable those that achieve remission to remain in remission for the long term.

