### **3. PATIENT SELECTION**

#### **3.1 Inclusion Criteria**

- 3.1.1. Patients must have a Confirmed diagnosis of non-M3 AML. Antecedent MDS is acceptable.
- 3.1.2. Post autologous Stem Cell Transplant Bone marrow biopsy core that is consistent with morphologic remission.
- 3.1.3. Age between 60 and 80years old.
- 3.1.4. Must have received induction and consolidation chemotherapy, and autologous stem cell transplant for AML.
- 3.1.5. Life expectancy of greater than 12 months.
- 3.1.6. Karnofsky Performance Status 70 or greater (see Appendix A)
- 3.1.7. Patients must have normal organ and marrow function as defined below:
  - Leukocytes  $\geq 2,000/\text{mCL}$
  - Absolute neutrophil count  $\geq 1,000/\text{mCL}$
  - Platelets  $\geq 75,000/\text{mCL}$
  - Total bilirubin  $\leq 4 \times$  institutional upper limit of normal unless 2nd to Gilbert's disease
  - AST(SGOT) and ALT(SGPT)  $\leq 4 \times$  institutional upper limit of normal
  - Creatinine  $< 1.5 \times$  institutional upper limit of normal OR creatinine clearance  $\geq 30 \text{ mL}/\text{min}/1.73 \text{ m}^2$  for patients with creatinine levels above institutional normal.
- 3.1.8 Able to take aspirin, or warfarin, or low molecular weight heparin as prophylactic anticoagulation.
- 3.1.9. Ability to understand and the willingness to sign a written informed consent document.
- 3.1.10 Must be registered into the mandatory RevAssist® program and be willing and able to comply with the requirement of RevAssist®.

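### The one-sample efficacy test has two unsourced no-drug relapse rates (90% and over 95%), and the protocol's own two-year data would beat both without lenalidomide

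*Combined protocol and SAP*

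**What the plan says.** Section 10.1, repeated in the Synopsis under Statistical Considerations, opens with estimation of two-year relapse-free survival (RFS) in about 30 patients. It adds a power claim of over 80%, "assuming 60% and 90% patients will relapse with and without lenalidomide, respectively". On the RFS scale that is 40% against 10%. The one-sample test of a proportion is then described as asking whether RFS with lenalidomide is "significantly higher than that without the treatment (relapse rate is expected to be >95" percent), which is an RFS below 5%. Alpha and sidedness are not stated.

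Section 2 gives these outcomes for patients over 60 without lenalidomide:

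- Autologous transplant, two years (Section 2.2): "The probability of 2 year leukemia-free survival was 39% for those candidate patients who underwent transplant", against 22% for those not transplanted.
- A second elderly transplant series (Section 2.2): "Leukemia free survival and overall survival at 3 years was 25% and 28% respectively".
- An induction-dose trial of 813 patients (Section 2.1): "Two year probabilities of relapse after CR for the standard versus intensified DNR groups were 61% versus 54" percent.

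Two statements point lower. The Synopsis says that "virtually all of those that achieve remission will relapse and die of their disease". Section 2.1 cites "3- and 5-year survival rates of only 9 to 10% and 3 to 8%, respectively, in patients over age 60".

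**The concern.** Efficacy is part of the primary objective (Section 1.1), and this is the only efficacy test the plan describes. There is no concurrent control, so the whole inference rests on the assumed no-drug rate. Two problems arise.

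First, the power sentence and the test sentence give different rates for that quantity, and the text does not say which one is tested.

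Second, both rates are far more pessimistic than the outcomes the protocol itself cites. The 60% relapse assumed with lenalidomide lies within the 54% to 61% quoted without it, and the implied 40% RFS is one point above the 39% reported after transplant alone. A trial that merely reproduced the cited transplant result would be declared a success, and the p-value could be reported as a lenalidomide effect when it reflects transplant and patient selection.

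**Working it through.** **Inputs.** n = 30 (Sections 5 and 10.1). Target RFS p1 = 1 − 0.60 = 0.40. Candidate nulls are p0 = 1 − 0.90 = 0.10 and, if the second rate is the null, p0 = 1 − 0.95 = 0.05. Because alpha is not given, one-sided 0.05 and 0.025 are both shown. No-drug scenarios from Section 2.2 are 39% (two years, transplanted), 25% (three years, transplanted, so a floor for that series at two years) and 22% (two years, not transplanted).

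**Method.** Exact binomial. The threshold k is the smallest count with P(X ≥ k | n = 30, p0) ≤ alpha. The probability of a significant result at true rate p is P(X ≥ k | 30, p).

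**1. The plan's own figures.** The power claim reproduces as a lower bound under either null, and the standard error at 40% is √(0.4 × 0.6 / 30) = 0.089, matching the stated limit of 9%. The arithmetic is not the fault.

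| Null RFS | One-sided alpha | Threshold | Actual size | Power at 40% |
|---|---|---|---|---|
| 10% | 0.05 | ≥7/30 | 0.026 | 0.983 |
| 10% | 0.025 | ≥8/30 | 0.008 | 0.956 |
| 5% | either | ≥5/30 | 0.016 | 0.998 |

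Five or six relapse-free patients would be significant against 5% and not significant against 10%.

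**2. Probability of significance if the drug is inactive.**

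| True RFS without drug effect | Null 10%, ≥7/30 | Null 10%, ≥8/30 | Null 5%, ≥5/30 |
|---|---|---|---|
| 39% | 0.978 | 0.945 | 0.998 |
| 25% | 0.65 | 0.49 | 0.90 |
| 22% (not transplanted) | 0.50 | 0.33 | 0.82 |

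**3. What a barely significant result would look like.** Against 5%, 5/30 (exact 95% CI 5.6% to 34.7%) and 6/30 (7.7% to 38.6%) both count as significantly higher, although both intervals lie below the cited 39%, the second only just.

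**4. Is 25% too high for a two-year rate?** No. Survival cannot rise with time, so 25% at three years means at least 25% at two. If the hazard does not increase over time, the two-year value lies between 25% (no events in year three) and 0.25^(2/3) = 39.7% (constant hazard).

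**5. Do the lower statements support 5% to 10%?** The Synopsis sentence has neither a source nor a time point. The figures of 9 to 10% and 3 to 8% are population-based overall survival at three and five years, not restricted to patients in remission. Neither describes two-year RFS in patients who are in remission after transplant.

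**6. Same test against a benchmark from Section 2.2, n = 30.**

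| Null RFS | One-sided alpha | Threshold | Power at 40% | True RFS for 80% power |
|---|---|---|---|---|
| 39% | 0.05 | ≥17/30 | 0.048 | about 62% |
| 39% | 0.025 | ≥18/30 | 0.021 | about 66% |
| 25% | either | ≥13/30 | 0.42 | about 49% |

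**The case against.** The strongest reply is that estimation is the stated aim and the test is an addition. The RFS estimate and interval do not depend on the null, no go/no-go decision is tied to the p-value, and 30 patients can be justified on precision. All of that stands, and it limits the damage to the inferential claim. It does not rescue the claim that relapse would be shown to be significantly reduced.

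The second rate can also be read as a parenthetical expectation, with 90% a conservative planning value. Power does hold under both. But the null is still unnamed, and the choice moves the threshold from 7 or 8 patients to 5.

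The benchmarks are imperfect. The 39% is quoted without a confidence interval, time origin or number transplanted. The 54% to 61% comes from an induction trial, so it is supporting evidence only. The 22% is for patients without transplant, whereas every participant here has had one. The populations differ in both directions. Required post-transplant remission and count recovery may raise the no-drug rate. This trial also takes patients up to age 80, does not require first remission, and states "Antecedent MDS is acceptable", while the 39% source is titled as de novo AML; these may lower it. These caveats weaken 39% as a fixed truth but do not bring the rate near 5% or 10%: the lowest of the cited figures, 22%, is still more than twice the larger null.

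Finally, no single-arm trial fully separates drug from selection. That is so, and it is a reason not to add a null that the cited data already exceed.

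**Conclusion.** The concern holds and should be fixed before the test is used. Section 10.1 gives two unsourced reference rates for one test, and both contradict Section 2. With an inactive drug the test would be significant with probability 0.945 to 0.998 if true RFS is 39%, and 0.49 to 0.90 if it is 25%. The ranges cover both nulls and both alpha levels. They assume 30 evaluable patients, an exact binomial test, and cited point estimates taken at face value. The stated power is correct arithmetic against the wrong reference.

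**What to change.** Amend Section 10.1 and the matching Synopsis text.

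**Preferred.** Delete the one-sample test and the power sentence. State that two-year RFS will be reported with its exact 95% CI (for 12/30, 22.7% to 59.4%) beside the cited historical figures, each with its time point and population, and that no formal comparison with a historical rate will be made. Justify 30 patients on precision (standard error 8.9% at 40%). Say how patients lost or withdrawn before two years are counted, since a simple binomial interval needs that rule.

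**If a test is kept.** Use one sourced two-year benchmark in both sentences, name alpha and sidedness, and restate power. The 25% figure should serve only as a labelled lower-bound sensitivity, because it is a three-year rate.

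**Cost.** The descriptive option needs text edits in two places and no added patients or procedures, but the plan loses its power statement. Keeping a test against 39% leaves 2% to 5% power at the 40% target, so the power rationale for 30 patients would go and the target itself would have to be reconsidered.

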### **10.2 Sample Size/Accrual Rate**

The primary and coordinating site will be the Montefiore-Einstein Cancer Center (MECC). The Bone Marrow Transplantation team at MECC sees on average 15 patients per year that would meet the eligibility criteria for the study.

We anticipate an annual accrual of 8 patients. The projected time for completion of the study is 45 months. Should the accrual be less than 8 patients per twelve month period from the start of activation of the protocol, we will be actively approaching other sites to participate in the study. Montefiore is a founding member of the Tri-State Transplant Consortium as well as a member of the Blood and Marrow Transplant Clinical Trials Network. Both of these cooperative groups may be utilized as sources of collaboration to boost accrual.

## **11 Data Management and Regulatory Requirements:**

Data on toxicities and patient outcomes will be collected at the individual participating institution treating the patient on protocol. Every 4 weeks the collected data will be submitted to the Montefiore-Einstein Cancer Center Research Study Coordinator [name]. Data submitted as Case Report Forms (CRF) will be submitted by participating institutions for central data management to the Montefiore-Einstein Cancer Center Research Study Coordination Center on a monthly basis, where they will be merged with the other data available for each study participant into one master data set.

### **11.1 Data Safety and Monitoring Plan**

During the recruitment and follow up phases of the trial, the Albert Einstein Cancer Center Data and Safety Monitoring Committee (DSMC) will monitor data and oversee patient safety. The principal investigator will participate in the meetings as a non-voting member. The DSMC meets every month and will review adverse events. DSMC will also review adherence to protocol and study progression on a quarterly basis. All adverse events will be reported, as per policy, to the CCI/IRB. The DSMC will make recommendations regarding study performance and continuation. [name] will provide requested data to the DSMC to assess progress toward resolving research questions.

In addition, [name] (PI) will review case report forms (CRFs) and any other toxicity data from all patients enrolled in this trial at regular frequent intervals. Biweekly conference calls will be conducted between the participating institutions to discuss trial patient enrollment, adverse events and protocol adherence.

Each participating investigator will have primary responsibility for the safety of individual participants under his/her care and will review the data and safety on an ongoing basis. In addition, the independent DSMC will have primary responsibility for monitoring the accumulating study data for signs of adverse trends in morbidity /

mortality and drug toxicity.

## **11.2 Recruitment and Consent**

Patients who are identified by clinicians at the participating sites as being eligible for the study will be approached by the local PI or co-PI about their potential participation. An informed consent document in English and Spanish will be provided to the patient. The investigational nature of the study, its objectives, the procedures and the potential risks and benefits involved will be explained to the patient in simple and direct lay language avoiding medical terms. The patient and the person taking the consent will sign the consent form and a copy of it will be given to the patient. A copy of the consent and the protocol will be left in the patient's chart.

## **11.3 Patient Protection**

This study will be conducted in compliance with the protocol, Good Clinical Practice and the applicable regulatory requirements. All research personnel will receive the required education and training needed for conducting clinical research related to the protection of human subjects and personal health information according to the Institutional Review board and the Health Insurance Portability and Accountability Act of 1996 Public Law 104-191. As mentioned above, each patient will be assigned a study identification number at the time of recruitment. Records will be kept confidential. As this research involves a drug, the U.S. Food and Drug Administration (FDA) may inspect the research records and medical records as may the Office for Human Research Protections (OHRP) and employees from Celgene Pharmaceutical Co, Ltd. The research study doctors and research staff will review medical records and will keep the information private. No patient will be identified in any written or verbal report with the following exception: the local human research committees of the participating institutions may inspect the patient records. All hard copies of information will be stored in locked cabinets, to which only senior research personnel has access. The study data files will be stored on password protected computers.

## **11.4 Record Retention:**

U.S. FDA regulations (21CFR312.62[c]) require all records and documents pertaining to the conduct of this study and the distribution of investigational drug, including CRFs, consents forms, laboratory test results and medication inventory records, must be retained by the Principal Investigator for 2 years after marketing application approval. If no application is filed, these records must be kept 2 years after the investigation is discontinued and the FDA and the applicable local health authorities are notified.

### **11.5 Study Monitoring:**

Site visits can be conducted by an authorized representative of the PI, [name] to inspect study data, subjects' medical records, and CRFs in accordance with ICH and GCP guidelines.

## APPENDIX A

### Performance Status Criteria

Karnofsky Performance Scale	
Percent	Description
100	Normal, no complaints, no evidence of disease.
90	Able to carry on normal activity; minor signs or symptoms of disease.
80	Normal activity with effort; some signs or symptoms of disease.
70	Cares for self, unable to carry on normal activity or to do active work.
60	Requires occasional assistance, but is able to care for most of his/her needs.
50	Requires considerable assistance and frequent medical care.
40	Disabled, requires special care and assistance.
30	Severely disabled, hospitalization indicated. Death not imminent.
20	Very sick, hospitalization indicated. Death not imminent.
10	Moribund, fatal processes progressing rapidly.
0	Dead.

